STUDY PROTOCOL

Use of transcutaneous electrical nerve stimulation (TENS) for the recovery of oral function after orthognathic surgery

NCT ID not yet assigned

05/11/2020

ABSTRACT:

Oral functions of patients are markedly diminished immediately after orthognathic surgery, and novel approaches are needed to accelerate their recovery. The aim of this study will be to examine the usefulness of weekly applications of transcutaneous electrical nerve stimulation (TENS) for this purpose, based on evidence of its effectiveness in other types of patients with muscle alterations. Maximum jaw opening, bite force, pain, and facial inflammation will be compared between patients receiving TENS and those receiving sham-TENS for 30 min at baseline and weekly over a four-week period after orthognathic surgery and will be also compared between before and after each procedure.

MATERIAL

The sample will be made up of a sufficient number of patients according to the calculation of the sample size who will undergo bimaxillary surgery or mandibular surgery divided between experimental (TENS group) and control groups (sham-TENS).

Participants will be selected by non-probabilistic sampling of consecutive patients until the estimated sample size is reached. All patients have a skeletal and facial deformity amenable to surgery after a pre-surgical orthodontic period, and they will have to signed their informed consent after receiving an information sheet on the study.

This study was approved by the ethics committee of the hospital (San Carlos Hospital, Madrid, Spain).

Inclusion criterion:

- programing of bimaxillary or mandibular orthognathic surgery by the same surgeon in order to avoid inter-operator variability.
- no surgery for temporomandibular disorders or more complex syndromes,
- no presence of muscle or nervous disorders or receipt of medication for such disorders

Exclusion criterion:

- the impossibility to attend follow-up appointments
- the refusal of informed consent.

The sample size will be estimated to obtain a statistical power of 80% with an alpha error of 0.05 and 95% confidence interval to detect a difference in jaw opening ≥ 2.5 mm.

Patients will be randomly assigned to the experimental group for TENS application or the control group for sham-TENS and will be blinded to their group assignation, as was the researcher responsible for data analyses (single-blind randomized clinical trial).

METHOD

TENS procedure

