An Enraf Nonius® S82 model TENS device will be used, with a maximum frequency of 220 Hz and an intensity range of 0 to 99.5 mA.

TENS electrodes will be placed bilaterally on mandibular elevator muscles, on the superficial masseter muscle above the gonial angle, and bilaterally on the anterior temporal muscle, following the manufacturer's instructions. The device will be applied in an identical manner to all patients in both groups and kept in position for the same time period (30 min); however, the device will be not switched on for the control group.

The stimulation intensity will be adjusted for those in the experimental group to the maximum that did not cause discomfort or areas of contraction, maintaining this stimulation intensity and frequency throughout the 30-min session.

Each participant will experience a weekly TENS or sham-TENS session on the same day of the week during a four-week period; appointments will be scheduled so as to minimize any possible interaction among study participants.

Study variables

Data will be gathered from all patients on jaw opening, bite force, inflammation, and pain before surgery and at 7, 14, 21, and 28 days post-surgery, conducting measurements both before and after the TENS/sham-TENS session.

Maximum Jaw Opening will be evaluated with patients seated vertically upright in the dental chair, using a digital dental caliber (Model R 100110, Mestra®) to measure the maximum opening from the incisal margin of upper central incisors to the incisal margin of lower incisors, adding the amount (in mm) of overbite or subtracting the amount (in mm) of open bite in occlusion.

Bite force will be measured using Dental Prescale Fuji® film, which is formed by microcapsules that generate a chemical reaction under pressure, staining the contact area with a color density corresponding to the pressure applied.

A sheet of the film will be placed between the occlusal surfaces of the two arches, and the patient will be asked to bite as strongly as possible for 5 sec. This procedure will be repeated three times, selecting the sheet with the best-defined tooth print to be photographed with a Canon® EOS 500 camera (RAW format, F32, and annular Flash) at the minimum distance permitted by the 75-macro lens.

The image will be processed in a Mac® computer to obtain the color value according to the Cie L*a*b* (CIELAB) scale, which gives the color a numerical value.

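### One of three bite-force sheets is kept by a subjective judgement, made before analysis by someone not stated to be unaware of the arm

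*Protocol*

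**What the plan says.** **Blinding.** The Protocol (MATERIAL) says that patients "will be blinded to their group assignation, as was the researcher responsible for data analyses (single-blind randomized clinical trial". No one else is named as blinded in the Protocol or in the SAP text available for review. One part of the SAP was not available, so nothing here is claimed about that part.

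**Visibility of the arm.** Under METHOD, TENS procedure, "the device will be not switched on for the control group", whereas "The stimulation intensity will be adjusted for those in the experimental group". Whoever operates the device can therefore tell the arms apart.

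**Bite force.** Under METHOD, Study variables, readings are taken at each visit, "conducting measurements both before and after the TENS/sham-TENS session". For the bite itself, "This procedure will be repeated three times", and one sheet goes forward: "selecting the sheet with the best-defined tooth print to be photographed". The film works by "staining the contact area with a color density corresponding to the pressure applied", and force is then pressure multiplied by the area of the print. The text does not say who chooses the sheet, what makes a print well defined, or what becomes of the other two.

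**Analysis.** The SAP (Statistical analysis) compares each measurement between arms with Student's t-test. It does not mention sheet selection.

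**The concern.** The choice of sheet is a judgement that fixes the data before the blinded analyst sees them. If the person choosing knows the arm, and if the print that looks best tends to be the one from the harder bite, a preference in one arm would raise that arm's bite force with no treatment effect. The analyst would receive one image per reading and could neither detect nor reverse this. The t-test would count it as an effect of TENS.

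The link between definition and force is plausible, because a harder bite gives a denser stain and force depends on both density and area. The Protocol does not demonstrate it. The rule may be meant only to secure a legible image.

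**Working it through.** **1. What the text establishes**

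| Step | Stated? |
|---|---|
| Patients blinded | Yes (MATERIAL) |
| Data analyst blinded | Yes (MATERIAL) |
| Device operator can see the arm | Follows from TENS procedure |
| Sheet selector unaware of the arm | Not stated |
| Working definition of the best print | Not given |
| Unchosen sheets photographed | Not planned |
| Selection precedes analysis | Yes (Study variables) |

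Bias in the comparison needs three further conditions, none of them shown: the selector knows the arm, definition tracks force, and the choice differs between arms.

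**2. Illustration of size**

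The plan gives no figure to reproduce. The available text states no N, SD or bite-force repeatability. The 0.05 level is from the SAP. Two-sided testing, 20 or 30 patients per arm, a repeat ICC of 0.7 to 0.9, and the degree of selection are assumptions.

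Let one sheet's value have total variance 1, with ICC between patients and 1 − ICC between repeats. There is no treatment effect. One arm takes the highest of three sheets with probability p and otherwise a random sheet. The other arm always takes a random sheet. The expected maximum of three standard normal values is 1.5/√π = 0.846, so

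bias = 0.846 × p × √(1 − ICC).

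| | ICC 0.7 | ICC 0.8 | ICC 0.9 |
|---|---|---|---|
| Bias in SD, p = 0.25 | 0.116 | 0.095 | 0.067 |
| Bias in SD, p = 0.5 | 0.232 | 0.189 | 0.134 |
| Type I error, n = 20, p = 0.25 | 6.6% | 6.1% | 5.6% |
| Type I error, n = 20, p = 0.5 | 11.1% | 9.0% | 6.9% |
| Type I error, n = 30, p = 0.25 | 7.2% | 6.6% | 5.6% |
| Type I error, n = 30, p = 0.5 | 14.5% | 11.4% | 8.1% |

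Type I errors are from 60,000 simulated trials per cell. Hand check of the largest: 0.232/√(2/30) = 0.232/0.258 = 0.90, and P(Z > 1.06) + P(Z < −2.86) = 0.145 + 0.002 = 0.147, against 0.145 simulated.

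A second model lets print definition correlate r with sheet-to-sheet force in one arm only. It gives nearly the same table with r in place of p. This is not independent support, because the mean bias has the same formula.

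If the correlation is 0.5 in *both* arms, the type I error is 4.8% to 5.1%. The same rule applied alike in both arms creates no bias between them.

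**3. Effect of averaging**

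The mean of three sheets has variance ICC + (1 − ICC)/3, against 1 for a single sheet chosen without regard to force: 0.800, 0.867 and 0.933 at ICC 0.7, 0.8 and 0.9. The variance of a patient's value thus falls by 20%, 13% and 7%. Only the repeat component shrinks. The between-patient component is unchanged. With averaging in both arms the type I error is 4.8% to 5.1%, provided selection was the only route of bias.

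**4. Number of images**

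One pre-surgery reading plus 4 visits × 2 = 9 readings, so 9 × 3 = 27 sheets, of which 9 are photographed as planned. Photographing all adds 27 − 9 = 18. If the pre-surgery visit also has two readings, there are 10 readings and 30 sheets, and the addition is 20.

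**The case against.** The strongest reply is that this is an argument from silence. The Protocol never says who chooses the sheet. Selection is described next to photography and image processing, so the blinded researcher may already do it, in which case the bite-force point falls away. The unavailable part of the SAP might also settle it. The rule reads naturally as a legibility rule, and the single-blind label makes no claim of assessor blinding. All of this stands, and it limits the point to a procedure that leaves an opening. What remains is that the Protocol prescribes a subjective choice without a criterion, and a concrete alternative is cheap.

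A reader might infer more: that the selector is the device operator, that the strongest print is being picked in the TENS arm, or that the trial's error rate is inflated. The documents support none of these. They do not identify the selector, do not equate definition with force, and give no figure from which a bias could be derived. Nor would knowledge gained by operating the device reach readings taken before a patient's first session.

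A reader might also infer that blinded sheet reading would secure the other outcomes. It would not. Biting and opening to the maximum depend on effort, and differential encouragement would be present in all three sheets. Caliper and ruler readings are not touched at all.

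**Conclusion.** The point holds in a limited form and is worth acting on. A subjective selection step precedes the blinded analysis of bite force, and in the available text the person making it is not said to be unaware of the arm. Harm is conditional on selection differing by arm.

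The range of 5.6% to 14.5% illustrates that condition under assumed sample size, repeatability and degree of selection. It is not an estimate for this trial. The upper end needs the larger sample, the lowest ICC and the strongest one-sided selection considered. With p or r at 0.25 the rate stays near 6% to 7%.

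For jaw opening, the outcome on which the trial is sized ("to detect a difference in jaw opening ≥ 2.5 mm"), and for swelling, the finding is only that the assessor's knowledge of the arm is unstated. That calls for clarification, not a change of design.

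**What to change.** Replace the choice of sheet with a rule that does not depend on who is present:

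- Label all three sheets of each reading with codes that hide patient, visit and arm, and keep the key from the person reading them.
- Photograph all three.
- Have the researcher already blinded for analysis either average all valid prints, or select one by a validity rule written in advance and applied alike in both arms (for example a complete print with no tear or smear).

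If the blinded researcher already selects the sheets, one sentence saying so, with the written criterion, would answer the selection point.

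**Cost.** Protocol wording, code labels, and 18 to 20 more images per patient to photograph and process. The bite-force value becomes a mean instead of a single-sheet value if averaging is chosen. The documents do not assign sheet reading to the blinded researcher, so the sponsor must confirm that this person can take it on.

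**Clarification only.** State whether those who measure jaw opening and swelling, and those who instruct patients during the bite, know the arm. Coding the sheets does not address bias by those routes.

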The corresponding pressure units (Megapascals, MPa) will be calculated according to Dental Prescale specifications, and the bite force (in Newtons [N]) will be obtained by using the following formula:

$$\text{Bite Force} = \text{Bite Pressure (MPa)} \times \text{mm}^2 \text{ print surface.}$$

Pain perceived by patients while autonomously opening and closing their jaws will be evaluated using a visual analog scale (VAS).

Facial inflammation will be measured (in mm) with patients seated upright in the dental chair, using a soft ruler to obtain a horizontal measurement from the lower border of the earlobe to the corner of the mouth and a vertical measurement from the gonial angle to the outer canthus of the eye. The soft ruler will be adapted to the contour of the patient's face without exerting any pressure.

All of the above measurements provided numeric values for treatment as continuous quantitative variables.

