### *Statistical analysis*

Descriptive statistics will be conducted to calculate distributions, frequencies, means and standard deviations for sex, malocclusion, and the results for maximum opening, bite force, inflammation, and pain in each group (experimental and control).

The Kolmogorov-Smirnov test will be applied to check the normality of variable distributions and Levene's test to check the equality of variances.

The Student's t-test will be employed to evaluate the difference in each measurement between experimental and control groups.

The paired Student's t-test will be used to compare measurements before and after TENS/sham-TENS in the same patient.

The GLM repeated-measures procedure will be applied to analyze the results for each group over time.

SPSS 22.0 ® for Windows will be used for statistical analysis

P≤0.05 was considered significant in all tests.

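### Facial inflammation is compared between arms as a raw distance with no baseline adjustment, so face size and any skeletal shift inflate the error variance, though they do not bias the randomised contrast

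*Protocol*

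**What the plan says.** The Protocol (Study variables) obtains inflammation from two distances. The first is "a horizontal measurement from the lower border of the earlobe to the corner of the mouth". The second, which uses a bony landmark of the lower jaw, is "a vertical measurement from the gonial angle to the outer canthus of the eye". The section then states: "All of the above measurements provided numeric values for treatment as continuous quantitative variables". Nothing is subtracted from the distances.

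Readings are scheduled "before surgery and at 7, 14, 21, and 28 days post-surgery". At the treatment visits they are taken twice, the protocol specifying "conducting measurements both before and after the TENS/sham-TENS session". The data therefore already include a pre-surgery distance and a day-7 distance taken before that day's session.

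The sample is made up of patients "who will undergo bimaxillary surgery or mandibular surgery divided between experimental (TENS group) and control groups (sham-TENS"), so an operation on the jaw lies between the pre-surgery reading and every later one.

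The SAP (Statistical analysis) plans three things:

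- a Student's t-test that "will be employed to evaluate the difference in each measurement between experimental and control groups";
- a paired t-test of before against after a session;
- a repeated-measures GLM for each group over time.

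It names no covariate, change score or reference visit for inflammation, and it does not list the visits that enter the GLM.

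**The concern.** A distance between two points on the face mostly reflects how large the face is; swelling adds a small amount to it. An unadjusted comparison of such distances carries all the between-patient variation in face size. Two of the landmarks, the gonial angle and the corner of the mouth, may also be moved by mandibular or bimaxillary surgery. That adds patient-to-patient variation after the operation that is not swelling.

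Two things are at stake. The between-arm comparison of one of the four outcomes named in the abstract may be too imprecise for a null result to mean anything, although readings that would remove most of the noise are already collected. And a comparison of a post-surgery visit with the pre-surgery visit within an arm would not measure swelling alone.

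**Working it through.** The supplied text gives no SD, effect size or sample size for inflammation, so there is no planned figure to reproduce. Every SD and correlation below is an assumption.

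**1. Variance model.** Let F be face size, K skeletal shift, S swelling and e reading error, mutually independent except that S at day 7 and day 28 may correlate (r).

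- Pre-surgery = F + e
- Day 7, before session = F + K + S7 + e
- Day 28 = F + K + S28 + e

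Assumed SDs: F 4-8 mm, K 0-5 mm, S7 3 mm, S28 1.5 mm, e 1.5 mm; r = 0 or 0.5.

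**2. One case in full: F = 6, K = 3, r = 0.5.**

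- Var(day 28) = 36 + 9 + 2.25 + 2.25 = 49.5
- Var(pre) = 36 + 2.25 = 38.25; Cov(pre, day 28) = Cov(pre, day 7) = 36
- Var(day 7) = 36 + 9 + 9 + 2.25 = 56.25; Cov(day 7, day 28) = 36 + 9 + 0.5 × 3 × 1.5 = 47.25

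Residual variance at day 28:

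- raw: 49.5 (SD 7.04)
- adjusted for pre-surgery: 49.5 − 36²/38.25 = 15.62 (SD 3.95)
- adjusted for day 7: 49.5 − 47.25²/56.25 = 9.81 (SD 3.13)
- adjusted for both: determinant 38.25 × 56.25 − 36² = 855.56; explained (56.25 × 36² − 2 × 36 × 36 × 47.25 + 38.25 × 47.25²)/855.56 = 41.87; residual 49.5 − 41.87 = 7.63 (SD 2.76)

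For equal precision, required sample size is proportional to residual variance (ignoring the two degrees of freedom spent on slopes). Raw against both: 49.5/7.63 = 6.5.

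**3. Across the range** (residual SD in mm):

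| F | K | r | raw | pre only | day 7 only | both | N ratio, raw : both |
|---|---|---|---|---|---|---|---|
| 4 | 2 | 0 | 4.95 | 3.24 | 3.42 | 2.90 | 2.9 |
| 6 | 2 | 0 | 6.67 | 3.26 | 3.64 | 2.91 | 5.3 |
| 6 | 0 | 0.5 | 6.36 | 2.57 | 3.09 | 2.28 | 7.8 |
| 6 | 3 | 0.5 | 7.04 | 3.95 | 3.13 | 2.76 | 6.5 |
| 8 | 5 | 0.5 | 9.67 | 5.63 | 3.23 | 3.02 | 10.2 |
| 8 | 0 | 0.5 | 8.28 | 2.58 | 3.19 | 2.28 | 13.1 |

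The first and last rows are the extremes of the grid, hence about 3 to 13. In every cell the raw analysis was worst, even with K = 0, and adjustment for both was best. Which single covariate is better depends on K: pre-surgery alone beats day 7 alone when K is about 1.5 mm or less (F 6-8, r = 0.5), or up to 2 mm when r = 0.

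**4. Bias between arms.** In 20,000 simulated trials with 20 per arm, simple randomisation, no treatment effect and a skeletal shift that depends on the procedure, the raw t-test rejected in 4.9% of runs, as did the test on change from pre-surgery. There is no inflation of type I error.

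**5. Within one arm, pre- to post-surgery.** Assume no swelling remains, 20 patients, shift SD 3 mm and error SD 1 mm per reading. The change then has SD √(9 + 1 + 1) = 3.32 and standard error 3.32/√20 = 0.74. A mean shift of 0 / 1 / 2 / 3 mm gave P≤0.05 in 5% / 25% / 73% / 97% of 4,000 runs.

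**The case against.** The strongest reply is that most of the planned inflammation analysis is unaffected. In the paired before/after-session test, face size and skeletal position cancel. In the repeated-measures GLM, within-patient contrasts remove face size and, among post-surgery visits, a fixed skeletal shift too. That stands. But the paired test covers change within a session, and the GLM is described for each group with no between-arm term stated. The only between-arm test named remains the unadjusted one.

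A reader might infer four stronger things that the documents do not support:

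- *That skeletal shift could imitate a treatment effect between arms.* Randomisation prevents this on average (step 4). Confusion with swelling is possible only in time comparisons that include the pre-surgery visit.
- *That the day-7 reading is the only usable reference.* With a small skeletal shift the pre-surgery reading does better, and using both is best throughout. Day 7 also contains swelling, so change from it measures resolution rather than amount.
- *That the plan will report change from before surgery as inflammation.* The SAP does not say which visits enter the GLM. Inclusion of the pre-surgery visit is an inference from the visit list, and no passage gives the size, direction or permanence of landmark movement.
- *That power for inflammation is known to be poor.* The sample size targets jaw opening, and without N, SD or an effect size for inflammation absolute power cannot be stated. Only the relative loss can be shown.

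It is also fair to say that the core remedy, baseline adjustment, would suit the other outcomes too. The case is sharper here because the raw reading is dominated by something other than the quantity of interest.

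**Conclusion.** The concern holds as one of precision, with a separate caution on interpretation. The unadjusted between-arm t-test on raw distances needs about 3 to 13 times as many patients as an analysis adjusted for both earlier distances. This rests on the assumed SDs and correlations above, none of which the documents give. The direction does not depend on skeletal movement, since the raw analysis is worst even when there is none. The randomised contrast is not biased and the paired session test is untouched. The caution on the time course applies only if the pre-surgery visit is included in it, and its size depends on an unknown mean shift. The change should be made, but the trial's validity does not hang on it.

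**What to change.** In the SAP, for each facial distance:

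1. Compare arms on the day 14, 21 and 28 readings by ANCOVA or a mixed model, with both the pre-surgery and the day-7 before-session distance as covariates.
2. Compare arms on the day-7 after-session reading with the same two covariates.
3. State which visits enter the time analysis, and do not interpret pre- to post-surgery change as swelling alone.

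Before this is fixed, reconcile the Protocol on when the first session takes place. The abstract describes sessions "for 30 min at baseline and weekly over a four-week period after orthognathic surgery", whereas the TENS procedure section describes one weekly session over four weeks and Study variables places the measured sessions at days 7 to 28. If a session precedes day 7, the day-7 reading is no longer pre-treatment; adjust for the pre-surgery distance and surgery type only.

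The cost is SAP wording, as all the readings are already scheduled. The downside is that the day-7 before-session reading becomes a covariate, so the first session's immediate effect is assessed separately from the later visits.
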